1.2.4. Treatment Toxicity

The dose-limiting factor associated with chemotherapy for GBM is bone marrow toxicity. Daily, low-dose TMZ given concomitantly with RT rarely affects platelet or neutrophil counts, but patients usually experience some degree of lymphopenia. In contrast, the standard TMZ dosing and schedule (Stupp et al 2005) used for adjuvant treatment frequently causes neutropenia and/or thrombocytopenia.

To achieve clinical benefit, it is imperative that the magnitude of any sensitizing effect for TMZ is significantly greater in the tumor than in the critical normal tissues. Targeting DNA repair pathways might be predicted to achieve tumor-specific chemo- and/or radio-sensitization.

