1.2.4.1. Toxicity of Dose-dense Temozolomide Regimens

Studies have been conducted to assess the safety concerns (Neyns et al 2010). The greater dose intensity achieved in these studies does not appear to significantly increase the frequency of

thrombocytopenia or neutropenia (Gilbert et al 2013). Available data from Phase 2 trials indicate a high incidence of lymphopenia (8% to 68%), a common TMZ toxicity, and a slight increase in fatigue. Grade 3 or 4 lymphopenia in trials using the 21 of 28 days TMZ schedule (75 mg/m²) occurred in 24% to 53% of cases, and Grade 4 lymphopenia, which may increase the risk of opportunistic infections, was reported in 47% in one study for recurrent anaplastic astrocytoma or oligoastrocytoma (Neyns et al 2008).

In the RTOG 0525 study, adverse events (AEs) were evaluated separately during the concurrent chemo- and radiotherapy and the adjuvant treatment phase. Grade 3 or 4 lymphopenia was the most common toxicity occurring in 12% of patients but without significant opportunistic infections. Serious neutropenia and thrombocytopenia occurred in 3.6% and 6.8%, respectively, of all patients undergoing RT. There was one treatment-related death as a result of neutropenia (Gilbert et al 2013).

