Several clinical studies have been conducted with PARP inhibitors (olaparib, rucaparib, and veliparib) in combination with TMZ. To determine the maximum tolerated dose (MTD) in these studies, TMZ was administered at standard doses (135 to 150 mg/m²/day or up to 1000 mg/m²/month) with increasing doses of the PARP inhibitor. All studies experienced the challenge of significant myelosuppression as dose-limiting toxicities (DLTs), and observed anti-tumor activity was only modest (Gabrielson et al 2015; Gojo et al 2017; Hussain et al 2014; Middleton et al 2015; Plummer et al 2013; Su et al 2014). This is contrasted by a recent study for talazoparib, a PARP inhibitor with very good DNA-trapping activity. Standard doses of talazoparib (0.5 to 1 mg) were administered with low doses of TMZ in patients with non-*BRC1/2*-mutated cancers (Wainberg et al 2016) The starting dose of TMZ was 25 mg/m², approximately 12.5% of the therapeutic dose, and the MTD was determined as 1 mg talazoparib plus 37 mg/m² of TMZ. This regimen was better tolerated than reported for prior studies, with less thrombocytopenia and neutropenia. Furthermore, promising efficacy was observed with 11 patients (61%) experiencing either a partial response or stable disease. These preliminary clinical results are in support of the hypothesis that PARP inhibitors with strong DNA-trapping activity may only require relatively low TMZ dose levels to exert their anti-tumor activity.

Ionizing radiation used in the clinical treatment of GBM generates mostly SSBs and to a minor extent DSBs. Single-strand breaks are repaired through the BER pathway, operating via either the *short patch* or the *long patch* repair sub-pathways, which differ in the size of the repair patch and the enzymes involved. A PARP-1 role in the *short patch* is well established, but its contribution in the *long patch* is still unclear. In non-replicating cells, PARP inhibition only delays the repair of SSBs

induced by radiation with a minimal impact on cell survival. On the contrary, PARP inhibition markedly enhances radiosensitivity of proliferating cells since unrepaired SSBs collide with the DNA replication machinery, generating DSBs. Thus, PARP inhibitors have the potential to increase the anti-tumor effect of RT by preventing DNA damage repair and increasing cytotoxic DNA damage (Godon et al 2008; Noel et al 2006; Dungey et al 2008).

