1.3.5.2. Exploratory Biomarker Data

1.3.5.3. Clinical Safety and Preliminary Efficacy for BGB-290-AU-002

BGB-290-AU-002 is a first-in-human trial evaluating pamiparib to characterize the safety, the MTD, preliminary anti-tumor activity and the pharmacokinetics of pamiparib given as a monotherapy in a 3+3 dose escalation scheme. Pamiparib was administered in doses ranging from 2.5 mg PO BID up to 120 mg PO BID.

The study is being conducted in 5 Australian study centers, and preliminary data for 45 patients are available (cutoff date of 30 September 2016).

The preliminary safety data indicate that the most frequent adverse events (AEs) ($\geq 10\%$ of patients) assessed as related to pamiparib were nausea (58%, n = 26), vomiting (51%, n = 23), fatigue (29%, n = 13), diarrhea (18%, n = 8), dry mouth (16%, n = 7) and decreased appetite (11%, n = 5).

Hematologic AEs are of interest in this study. The most frequent hematologic AEs ($\geq 10\%$ of patients) assessed as related to pamiparib were anemia (22%, n = 10) and neutropenia (11%, n = 5).

Hematologic AEs, regardless of relatedness, were reported in 40% of patients (n = 18). Anemia was most frequent (33%, n = 15), followed by neutropenia (11%, n = 5) and thrombocytopenia (2%, n = 1).

Twenty-six patients experienced Grade 3 AEs (regardless of relatedness), and no Grade 4 AEs were reported. Eleven Grade 3 AEs in 9 patients (20%) were considered related to pamiparib: anemia (n = 5), neutropenia (n = 3), hypophosphatemia (n = 1), nausea (n = 1) and fatigue (n = 1). Serious AEs (SAEs) reported as related to pamiparib included anemia (n = 2) and nausea (n = 1).

SAEs were reported in 25 patients, and for 3 patients they were considered related to BGB 290: anemia (n = 2) and nausea (n = 1). Three patients discontinued study drug because of an AE: vomiting (n = 1), oral paresthesia (n = 1), and right neck cutaneous metastases (n = 1).

Four patients experienced a fatal AE \leq 28 days after the last pamiparib dose. All deaths were due to complications of the underlying malignancy, and none was considered related to pamiparib.

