4.2.4. Definition of Dose-Limiting Toxicity

A DLT is defined as one of the following toxicities occurring during the DLT assessment window (as defined for each of the arms and cohorts; [Section 4.2.3](#)) and considered by the investigator to be related to pamiparib:

- Grade ≥ 3 non-hematologic, non-hepatic major organ AE, with the following exceptions:
 - Grade 3 nausea, vomiting, or diarrhea that resolves to Grade ≤ 1 with optimal medical management within 3 days
 - Grade 3 electrolyte disturbances that respond to correction within 3 days
- Grade 4 neutropenia lasting > 7 days
- Grade ≥ 3 febrile neutropenia
- Grade 3 thrombocytopenia with clinically significant bleeding
- Grade 4 thrombocytopenia lasting > 3 days and requiring transfusion, or any decreased platelet count $< 15,000/\text{mm}^3 / < 15.0 \times 10^9/\text{L}$
- Grade ≥ 4 anemia
- Grade ≥ 3 total bilirubin or hepatic transaminases (ALT [SGPT] or AST [SGOT]) with the following exceptions:
 - For patients with Grade 1 hepatic transaminase levels at baseline, a hepatic transaminase level of $> 7.5 \times$ upper limit of normal (ULN) will be considered a DLT.

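### Protocol 4.2.4 is not monotone in severity: a clinically significant bleed is a DLT with Grade 3 thrombocytopenia, but in a narrow band of Grade 4 cases the same bleed is not

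*Protocol*

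**What the plan says.** Protocol 4.2.4 lists the toxicities that count as DLTs when they fall in the assessment window and the investigator judges them related to pamiparib. Two bullets concern platelets:

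- "Grade 3 thrombocytopenia with clinically significant bleeding", with no condition on duration, transfusion or grade of bleed.
- "Grade 4 thrombocytopenia lasting > 3 days and requiring transfusion, or any decreased platelet count" below 15 × 10⁹/L. Bleeding is not mentioned.

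Elsewhere the list uses the ≥ sign when it means that grade or worse, as in "Grade ≥ 3 febrile neutropenia" and in the anemia and hepatic bullets. The first bullet separately captures Grade ≥3 non-hematologic AEs in a major organ, which would include a severe bleed.

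Protocol Table 4 sets the platelet limits: Grade 3 is <50 to 25 × 10⁹/L and Grade 4 is <25. Protocol 4.2.2 uses the DLT count to escalate, expand or stop, and so to declare the MTD or MAD. SAP 6.5.2 summarises, by cohort and arm, the DLT events recorded on the AE eCRF. It neither restates nor amends the definition.

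**The concern.** A toxicity definition should not count a milder event and pass over a worse one. Here the bleeding criterion is tied to exactly Grade 3, and the Grade 4 bullet sets different conditions, so a bleed can lose DLT status because the platelet count fell further.

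What is at stake is the count that fixes the MTD or MAD. The consequence can cross arms: the TMZ dose judged safe in Arm C caps the first TMZ dose in Arm B (4.2.1) and the maintenance dose in Arms A and B (4.1.1).

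An affected patient may also leave the denominator. Table 4 holds both drugs for Grade 4 platelets until recovery to Grade ≤1 or baseline. Protocol 4.2.3 makes a patient without a DLT non-evaluable, and replaceable, if less than 70% of scheduled drug is received in the window.

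**Working it through.** There is no stated sample size, power or error rate to reproduce. The check applies the text of 4.2.4 with the Table 4 limits.

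**Step 1: enumerate the rule.** Take a pamiparib-related, clinically significant bleed in the window, occurring only at the stated platelet level. Cross platelets (30, 20, 12 × 10⁹/L), duration (2 or 5 days), transfusion (yes or no) and whether the bleed is a Grade ≥3 major organ AE (yes or no). That gives 3 × 2 × 2 × 2 = 24 combinations.

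| Platelets | Grade | Combinations | DLT | Not a DLT |
|---|---|---|---|---|
| 30 | 3 | 8 | 8 | 0 |
| 20 | 4 | 8 | 5 | 3 |
| 12 | 4 | 8 | 8 | 0 |

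The three that escape all have platelets of 20 and a bleed that is not a Grade ≥3 major organ AE: 2 days without transfusion, 2 days with transfusion, and 5 days without transfusion. So 13 of the 16 Grade 4 combinations are DLTs. These counts describe the logic of the rule; they are not patient frequencies.

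**Step 2: state the gap.** The event is not a DLT when all of these hold: the platelet nadir is 15 to <25; bleeding occurs only while platelets are <25 (bleeding at 25 to <50 meets the Grade 3 bullet); the Grade 4 episode lasts ≤3 days or needs no transfusion; and the bleed is not a Grade ≥3 major organ AE.

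**Step 3: effect of one uncounted case under 4.2.2.** Counting it would turn 0/3 into 1/3, which means expanding to 6 instead of being free to escalate. It would turn 1/6 (16.7%) into 2/6 (33.3%), which reaches the one-third limit and means the MTD is exceeded.

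**Step 4: evaluability.** In Arm C, TMZ is given on 21 days of the 28-day window, and 70% of 21 is 14.7 days. Missing 7 days leaves 14, which is below the limit. A Grade 4 hold could therefore make an uncounted case non-evaluable.

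**Step 5: frequency.** No rate for this class appears in either document. The background is mixed:

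- On pamiparib alone, any-grade thrombocytopenia occurred in 1 of 45 patients (2.2%; exact 95% CI 0.06% to 11.8%), and "no Grade 4 AEs were reported" (Protocol 1.3.5.3).
- In the dose-dense TMZ trial, serious thrombocytopenia occurred in 6.8% (1.2.4.1), while daily low-dose TMZ with RT "rarely affects platelet or neutrophil counts" (1.2.4).
- Protocol 1.3.3 reports dose-limiting myelosuppression when PARP inhibitors were combined with standard-dose TMZ, but better tolerance and less thrombocytopenia with low-dose TMZ, which is the approach taken here.

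None of these figures gives the share of cases that would meet every condition in Step 2.

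**The case against.** The strongest reply is that Grade 3 is drafting shorthand: a bleed that qualifies at Grade 3 qualifies all the more at Grade 4, and the next bullet only adds Grade 4 events without bleeding. That is a plausible intent, but the text does not say it, and the use of ≥ in neighbouring bullets points the other way.

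The second reply is that safeguards exist. Before each escalation step the team reviews AEs and laboratory data (4.2.2). Table 4 requires a hold and a TMZ reduction for Grade 4 platelets. Expansion accrual halts if Grade ≥3 toxicities suggest the MTD was exceeded (4.3). SAP 6.5.3 and 6.5.4 will report Grade ≥3 TEAEs, dose changes, all AEs and worst platelet grade. This stands, and it is why the impact is low. These outputs would show the parts of such an event, but nothing would identify it as missing from the DLT summary.

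Third, a retrospective check has limits. Scheduled hematology is about weekly on treatment and two-weekly in the Rest phase, which falls inside the longer Arm A windows (for example, the 10-week window of Cohort 3). Without unscheduled draws, whether an episode lasted ≤3 days often cannot be settled. This also stands.

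A reader might infer that bleeding with Grade 4 thrombocytopenia is generally not a DLT. It usually is, through one of the other routes in Step 1.

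**Conclusion.** As written, 4.2.4 misclassifies a narrow class of events in the count that sets the MTD or MAD, and no other section of the protocol or SAP corrects it. This rests on a literal reading of the bullets and the Table 4 cut-offs.

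The frequency is unknown and likely low, since several conditions must hold together. Any stated chance of an uncounted case would rest on an invented rate, so none is offered. A reader might also infer that DLTs were missed or that the selected doses are too high. The documents do not support that: neither shows that such a case occurred.

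Practical impact is low. AE and laboratory data inform each escalation decision, and SAP 5 reports Phase 1b complete at 46 patients. The case for acting is that the correction is nearly free and would let the reported DLT count be read without this doubt.

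**What to change.** For any further escalation, change Grade 3 to Grade ≥3 in the bleeding bullet of 4.2.4.

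For the completed Phase 1b, review the existing AE and platelet data for all 46 dosed patients, including those replaced or not DLT-evaluable. In the DLT summary, footnote any Grade 4 thrombocytopenia with clinically significant bleeding in the DLT window that was not counted as a DLT, by cohort and arm, or state that none was identified. Add that platelet sampling may not resolve episode duration.

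The cost is one symbol, a small cross-check of data the SAP already tabulates or lists, and a footnote. The footnote would not itself change the formal DLT count, the MTD or the MAD. The downside of the corrected bullet is a slightly more conservative rule in any further escalation.

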4.3. Details of Cohort-Expansion Stage

Expansion cohorts (up to approximately 60 patients each) may be enrolled at a dose level below or equal to the MTD or MAD of pamiparib (Arm A) or TMZ (Arms B and C) to better characterize the safety and tolerability of pamiparib in combination with RT, RT and TMZ or TMZ alone, and to make a preliminary determination of the efficacy of these combinations.

Arms A and B may have one expansion cohort each, and only patients with unmethylated GBM will be allowed to enroll. After dose escalation in Arm C for GBM patients regardless of *MGMT* methylation status, Arm C may have two expansion cohorts, one for unmethylated GBM and one for methylated GBM.

The rules for continued dosing in the cohort-expansion stage will be identical to those in the dose-escalation stage.

If the frequency of Grade ≥ 3 toxicities or other unacceptable chronic toxicities in the cohort expansion stage of a given arm suggest that the MTD has been exceeded at that dose level, any remaining accrual at that dose level will be halted. Consideration will then be given to enrolling additional patients (up to approximately 60 patients) into an expansion cohort at a lower dose level.

4.4. Duration of Study

[figure not shown]
The duration of the study from first enrolled patient to final analysis of OS is estimated to be approximately 4 years.

5. STUDY POPULATION

5.1. Inclusion Criteria

Patients must meet all of the following criteria to be eligible for the study:

For all patients

1. Signed Informed Consent Form (ICF)
2. Age ≥ 18 years
3. Histopathologically confirmed glioblastoma (World Health Organization [WHO] Grade IV) ([Louis et al 2016](#))
 - Tumor must have a supratentorial component.
4. 
5. Ability to undergo serial MRI scans (computerized tomography [CT] cannot substitute for MRI)
6. Brain MRI scan ≤ 14 days prior to Day 1
 - Patients requiring glucocorticoids must be on a daily dose equivalent of dexamethasone 4 mg twice daily or less that has been stable for ≥ 7 days prior to the MRI
7. ECOG performance status ≤ 1 ([Appendix 3](#))

8. Ability to swallow whole capsules
9. Adequate hematologic and end-organ function, as defined by the following laboratory results (obtained ≤ 2 weeks prior to Day 1):
 - Absolute neutrophil count (ANC) $\geq 1.5 \times 10^9/L$
 - Platelet count $\geq 100 \times 10^9/L$
 - Hemoglobin ≥ 9 g/dL ≥ 14 days after growth factor support or transfusion if appropriate
 - Serum creatinine $\leq 1.5 \times$ ULN or estimated creatinine clearance ≥ 50 mL/min (calculated using the institutional standard method)
 - Total serum bilirubin $\leq 1.5 \times$ ULN ($\leq 4 \times$ ULN, if Gilbert's syndrome)
 - Aspartate and alanine aminotransferase (AST and ALT) $\leq 3 \times$ ULN
 - Albumin ≥ 3 g/dL
 - International Normalized Ratio (INR) ≤ 1.5 and activated partial thromboplastin time (aPTT) $\leq 1.5 \times$ ULN
10. Female patients of childbearing potential and female partners of male study patients must agree to practice highly effective methods of birth control ([Appendix 4](#)) for the duration of the study, and for ≥ 6 months after last study treatment. In addition, non-sterile male patients must agree to practice highly effective methods of birth control ([Appendix 4](#)) and avoid sperm donation for the duration of the study and for ≥ 6 months after the last dose of study drug.
11. Willingness and ability to comply with all protocol-specified requirements
 - **For patients in Arms A and B (NOT applicable to Arm C)**
 - 12. No previous treatment except surgery (ie, no previous RT, local chemotherapy, or systemic therapy for lower grade central nervous system tumors)
 - 13. Ability to initiate RT ≤ 49 days after surgery, but ≥ 14 days after a biopsy or ≥ 28 days after an open biopsy or a craniotomy with adequate wound healing
 - 14. Documentation of unmethylated *MGMT* promoter status
 - In escalation cohorts, it is preferable to determine *MGMT* status by quantitative methylation-specific polymerase chain reaction (MS-PCR). Other acceptable platforms include pyrosequencing methodologies and methylation sensitive high-resolution melting (MS-HRM) assays with comparable sensitivity, applied to archival or fresh tumor tissue. Sponsor must be notified prior to utilizing alternate assays or if data from acceptable alternate platforms are available.
 - In expansion cohorts, archival or fresh tumor tissue must be submitted for central analysis of *MGMT* status.

→ For patients in Arm C Escalation (*NOT applicable to Arms A and B*)

15. Documentation of *MGMT* promoter status
 - It is preferable to determine *MGMT* status by MS-PCR. Other acceptable platforms include pyrosequencing methodologies and MS-HRM assays with comparable sensitivity, applied to archival or fresh tumor tissue. Sponsor must be notified prior to utilizing alternate assays or if data from acceptable alternate platforms are available.
16. No prior systemic chemotherapy, other than TMZ, for glioblastoma (including investigational cytotoxic chemotherapy) and no prior anti-angiogenic therapy
 - Prior use of Optune device is allowed with a minimum of 1 week since last Tumor Treating Fields application
17. Histologically confirmed *secondary* glioblastoma will be allowed during the dose escalation phase only
18. Disease that is evaluable or measurable as defined by Response Assessment in Neuro-Oncology (RANO) criteria ([Appendix 2](#))

→ For patients in Arm C Expansion

19. Histologically confirmed *de novo* (primary) glioblastoma with unequivocal first progressive disease (PD) after RT with concurrent/adjuvant TMZ chemotherapy as defined by one or more of the following:
 - PD \geq 3 months after the end of radiotherapy
 - PD that is clearly outside the radiation field
 - PD that has been unequivocally proven by surgery/biopsy
20. Disease that is measurable as defined by RANO criteria ([Appendix 2](#))
 - Patients with recurrent disease must have at least one bi-dimensionally measurable contrast-enhancing lesion with clearly defined margins by MRI scan, with minimal diameters of 10 mm, visible on 2 or more axial slices
21. Documentation of *MGMT* promoter status
 - Tumor tissue (archival or fresh) must be submitted for central analysis of *MGMT* status
 - Patients will be enrolled into 1 of 2 expansion cohorts based on *MGMT* methylation status

5.2. Exclusion Criteria

Patients will be excluded from the study for any of the following reasons:

For all patients

1. Chemotherapy, biologic therapy, immunotherapy, or investigational agent ≤ 21 days (or ≤ 5 half-lives, whichever is shorter) prior to Day 1
2. Unresolved acute effects of any prior therapy of Grade ≥ 2 , except for AEs not constituting a safety risk by investigator judgement
3. Major surgical procedure, open biopsy, or significant traumatic injury ≤ 28 days prior to Day 1, or anticipation of need for major surgical procedure during the course of the study
 - Placement of vascular access device is not considered major surgery.
4. Other diagnosis of malignancy
 - Except for surgically excised non-melanoma skin cancer, adequately treated carcinoma in situ of the cervix, localized prostate cancer treated with curative intent, adequately treated low-stage bladder cancer, ductal carcinoma in situ treated surgically with curative intent, or a malignancy diagnosed > 2 years ago with no current evidence of disease and no therapy ≤ 2 years prior to Day 1
5. Active infection requiring systemic treatment
6. Have known human immunodeficiency virus (HIV) infection or serologic status reflecting active viral hepatitis infection:
 - Patients with untreated chronic hepatitis B or chronic hepatitis B virus (HBV) carriers whose HBV DNA is > 500 IU/mL or patients with active hepatitis C virus (HCV) should be excluded. Note: Inactive hepatitis B surface antigen (HBsAg) carriers, treated and stable hepatitis B (HBV DNA ≤ 500 IU/mL), and cured patients with hepatitis C can be enrolled.
7. Any of the following cardiovascular criteria:
 - Current evidence of cardiac ischemia
 - Current symptomatic pulmonary embolism
 - Acute myocardial infarction ≤ 6 months prior to Day 1
 - Heart failure of New York Heart Association Classification III or IV (see [Appendix 5](#)) ≤ 6 months prior to Day 1
 - Grade ≥ 2 ventricular arrhythmia ≤ 6 months prior to Day 1
 - Cerebral vascular accident (CVA) or transient ischemic attack (TIA) ≤ 6 months prior to Day 1
8. Active inflammatory gastrointestinal disease, chronic diarrhea, known diverticular disease or previous gastric resection or lap-band surgery
 - Gastroesophageal reflux disease under treatment with proton-pump inhibitors is allowed (assuming no drug interaction potential)

9. Active bleeding disorder, including gastrointestinal bleeding, as evidenced by hematemesis, significant hemoptysis or melena \leq 6 months prior to Day 1
10. Anticoagulation with heparin, warfarin, or other anticoagulants other than the following:
 - Low-dose aspirin and/or non-steroidal anti-inflammatory agents are allowed
 - Use of thrombolytics to establish patency of indwelling venous catheters is allowed
 - Prophylactic anticoagulation for venous access devices is allowed as long as INR is \leq 1.5 and aPTT \leq 1.5 \times institutional ULN
 - Low molecular weight heparin for treatment of thromboembolic events
11. Use \leq 10 days (or \leq 5 half-lives, whichever is shorter) prior to Day 1 or anticipated need for food or drugs known to be strong or moderate CYP3A inhibitors or strong CYP3A inducers including known enzyme inducing anti-epileptic drugs ([Appendix 6](#))
12. Pregnancy or nursing
 - Females of childbearing potential require a negative serum pregnancy test \leq 7 days before Day 1
13. Significant intercurrent illness that may result in the patient's death prior to death from glioblastoma
14. Known history of intolerance to the excipients of the pamiparib capsule
 - **For patients in Arms B and C (NOT applicable to Arm A)**
 - 15. Known hypersensitivity to any temozolomide component or to dacarbazine (DTIC)
 - 16. Have hereditary problems of galactose intolerance, the Lapp lactase deficiency, or glucose-galactose malabsorption

